	The secondary objectives are to:		
	Evaluate the effects of neflamapimod on informant/caretaker evaluation of cognition and function, as assessed by the Clinical Dementia Rating Scale-Sum of Boxes (CDR-SB).		
	Assess the effects of neflamapimod on general cognition, as assessed by the Mini Mental State Examination (MMSE).		
	Assess the effects of neflamapimod on episodic memory, as assessed by the International Shopping List Test (ISLT).		
	 Assess the effects of neflamapimod on select domains of the 10-item Neuropsychiatric Inventory (NPI-10), including depression (dysphoria), anxiety, hallucinations, and agitation/aggression. 		
	 Evaluate the effects of neflamapimod on motor function as assessed by the Timed Up and Go Test (TUG). 		
	• Evaluate the effects of neflamapimod on quantitative electroencephalography (EEG) parameters.		

Study Endpoints	Primary endpoints:		
	Change in the composite score of the NTB, including assessments of attention, executive function, and visuospatial function in neflamapimod treated-subjects as compared to the placebo-treated subjects.		
	Secondary endpoints:		
	Change in CDR-SB in neflamapimod-treated subjects compared to placebo- recipients.		
	 Change in MMSE in neflamapimod-treated subjects compared to placebo- recipients. 		
	Change in NPI-10 domains in neflamapimod-treated subjects compared to placebo-recipients.		
	Change in International Shopping List Test immediate & delayed recall and recognition in neflamapimod-treated subjects compared to placebo-recipients.		
	Change in Timed Up and Go Test.		
	Change in EEG parameters.		
Number of Subjects	80 subjects are planned to be enrolled		
Subject Population	Subjects aged ≥55 years with mild-to-moderate (MMSE 15-28) probable DLB by consensus criteria (McKeith et al, 2017), including a positive DaTscan TM , who are currently receiving cholinesterase inhibitor therapy. If the DaTscan is negative, but the subject has historical polysomnography (PSG)-verified REM sleep behavioral disorder (RBD), this will also qualify as probable DLB.		
Inclusion Criteria	1. Men and women aged ≥55 years.		
	2. Subject or subject's legally authorized representative is willing and able to provide written informed consent.		

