4.2. Exclusion Criteria

Subjects meeting any of the following criteria are not eligible for enrollment in this study:

- 1. Diagnosis of any other ongoing CNS condition other than DLB, including, but not limited to, post-stroke dementia, vascular dementia, AD, or PD.
- 2. Suicidality, defined as active suicidal thoughts within 6 months before Screening or at Baseline, defined as answering yes to items 4 or 5 on the Columbia-Suicide Severity Rating Scale (C-SSRS), or history of suicide attempt in previous 2 years, or, in the Investigator's opinion, at serious risk of suicide.
- Ongoing major and active psychiatric disorder and/or other concurrent medical condition that, in the opinion of the Investigator, might compromise safety and/or compliance with study requirements.
- 4. Diagnosis of alcohol or drug abuse within the previous 2 years.

- 5. Poorly controlled clinically significant medical illness, such as hypertension (blood pressure >180 mmHg systolic or 100 mmHg diastolic); myocardial infarction within 6 months; uncompensated congestive heart failure or other significant cardiovascular, pulmonary, renal, liver, infectious disease, immune disorder, or metabolic/endocrine disorders or other disease that would interfere with assessment of drug safety.
- 6. Aspartate aminotransferase (AST) or alanine aminotransferase (ALT) > 2 × the upper limit of normal (ULN), total bilirubin > 1.5 × ULN, and/or International Normalized Ratio (INR) > 1.5.
- 7. Known human immunodeficiency virus, hepatitis B, or active hepatitis C virus infection.
- 8. Participated in a study of an investigational drug less than 3 months or 5 half-lives of an investigational drug, whichever is longer, before enrollment in this study.
- 9. History of previous neurosurgery to the brain.
- 10. If male with female partner(s) of child-bearing potential, unwilling or unable to adhere to contraception requirements specified in the protocol.
- 11. If female who has not has not reached menopause >1 year previously or has not had a hysterectomy or bilateral oophorectomy/salpingo-oophorectomy, has a positive pregnancy test result during Screening and/or is unwilling or unable to adhere to the contraception requirements specified in the protocol.

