5.8. Contraception and Pregnancy

This section should be read in conjunction with the selection criteria that relate to age and contraception:

• Exclusion criteria #10 and #11 (Section 4.2)

No signs of embryo-fetal toxicity or teratogenic effects of neflamapimod were observed in rats. Testing in rabbits was not performed due to lack of exposure following administration of the neflamapimod formulation. No human studies of effects of neflamapimod on conception, pregnancy, or lactation have been performed. Females should not be exposed to neflamapimod if pregnant, breastfeeding, or attempting to conceive. The following guidelines for contraception should be followed from before first dose on Day 1 through 91 days following the last dose of study drug:

Female subjects of child-bearing potential (have not experienced menopause and have not had a hysterectomy or bilateral oophorectomy/salpingo-oophorectomy) or female subjects who have experienced menopause within the previous year must have a negative pregnancy test during Screening and must use at least 1 of the following contraceptive methods: complete abstinence regardless of menstrual cycle timing, contraceptive (oral, transdermal, injectable, or implantable), intrauterine device, or barrier method of contraception.

Male subjects with female partners of child-bearing potential must use at least 1 of the following contraceptive methods: hormonal contraceptives (oral, injectable, patch, intrauterine devices), male sterilization, or total abstinence from heterosexual intercourse, when this is the preferred and usual lifestyle of the subject.

• Abstinence is defined as refraining from heterosexual intercourse during the entire period of risk associated with the study treatments when this is the preferred and usual lifestyle of the subject.

Note that periodic abstinence (calendar, symptothermal, post-ovulation methods), withdrawal (coitus interruptus), spermicides only, and lactational amenorrhoea method are not acceptable methods of contraception.

Any pregnancy should be reported to the Investigator, and, in turn, the pregnancy should be reported to Worldwide Clinical Trials within 24 hours of the Investigator's awareness of the pregnancy. If a female

subject becomes pregnant, study drug will be permanently discontinued and the subject will be discontinued from the study.

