- a. One to two Screening visits are planned during which safety screening procedures are to be completed and reviewed, including a practice NTB and the required diagnostic and cognitive impairment procedures. Screening will be conducted within 21 days before Baseline (Day 1); if a DaTscan and/or MRI or CT scan is required to determine study eligibility, Screening may be extended to 35 days. (If necessary, a second visit may be conducted on a different day to allow for scheduling purposes.) All screening assessments should be conducted within 21-35 days of Day 1 and can be condensed to one visit
- b. On Day 1, all procedures should be conducted prior to first dose of study drug.
- c. Subjects who prematurely discontinue study drug for any reason will be asked to return to the study center for an Early Termination visit within 3 days following the last study drug dose; if it is determined that the subject will discontinue study drug while at the study center for a scheduled visit, then the Early Termination visit should be conducted at that time.
- d. The Follow-up Visit should be conducted within 14 (±3) days of the last dose of study drug for subjects who complete the study or discontinue early.
- e. Informed consent procedures, including signing of informed consent, must be completed before any study-specific procedures are performed.
- f. Female subjects who have reached menopause in the previous year must have a serum or urine pregnancy test performed during Screening; subjects with positive results are not eligible for study participation.
- g. Refer to Section 6.2.8 for details regarding physical examination.
- h. Vital signs include blood pressure, pulse, respiratory rate, and body temperature. Vital signs should be measured after the subject has been in sitting position for 5 minutes.
- i. Details of clinical laboratory sampling for chemistry, hematology, and coagulation studies are discussed in Section 6.2.10.
- j. Details of 12-lead ECG assessment are discussed in Section 6.2.9.
- k. Subjects are required to have a prior DaTscan. If a DaTscan has not been performed within the previous 2 years, it is to be performed during Screening only after subject has been deemed eligible based on all other inclusion/exclusion criteria (e.g., medical history, laboratory testing) and prior to randomization. Note that if DaTscan results are negative (i.e., no evidence of

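### Table 6-1 footnote f names fewer women for the Screening pregnancy test than Section 5.8 does, and the two are not linked

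*Protocol*

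**What the plan says.** Three places in the protocol bear on the Screening pregnancy test.

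- **Table 6-1, footnote f (Section 6.1).** "Female subjects who have reached menopause in the previous year must have a serum or urine pregnancy test performed during Screening". It adds that "subjects with positive results are not eligible for study participation".
- **Section 5.8.** The test is required in two groups. The first is described as "Female subjects of child-bearing potential (have not experienced menopause and have not had a hysterectomy or bilateral oophorectomy/salpingo-oophorectomy". The second is joined to it in the same sentence: "female subjects who have experienced menopause within the previous year must have a negative pregnancy test during Screening". The section also states that "Females should not be exposed to neflamapimod if pregnant, breastfeeding, or attempting to conceive".
- **Exclusion criterion 11 (Section 4.2, repeated in the Synopsis).** It opens "If female who has not has not reached menopause >1 year previously or has not had a hysterectomy or bilateral oophorectomy/salpingo-oophorectomy" and excludes such a woman if she "has a positive pregnancy test result during Screening", or if she will not or cannot follow the contraception requirements.

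Inclusion criterion 1 sets the age range: "Men and women aged ≥55 years".

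**The concern.** Footnote f is the only note in the schedule that says which women are tested, and it leaves out one of the two groups in Section 5.8. The omitted group is the women who have not yet reached menopause. If such a woman is not tested, the positive-test part of exclusion 11 cannot come into play for her. She could then start a drug for which Section 5.8 reports no human data on conception, pregnancy or lactation, without the negative result that the same section requires. At stake are eligibility and the safety of a small number of subjects. Power, the estimand and the analysis are not affected.

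**Working it through.** No arithmetic applies. The check is to compare the three passages group by group.

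| Group of women | Footnote f | Section 5.8 | Exclusion 11 |
|---|---|---|---|
| Not yet at menopause, no hysterectomy or bilateral oophorectomy | Not named | Negative test required | Covered |
| Menopause within the previous year | Test required | Negative test required | Covered |
| Menopause more than one year ago | Not named | Not named | Not the group in question |

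1. In the second row all three passages agree.
2. In the third row footnote f and Section 5.8 agree, since neither asks for a test.
3. In the first row Section 5.8 orders a test and footnote f does not mention the group. The mismatch between the two is confined to this row.
4. Exclusion 11 is loosely worded where it joins the menopause clause to the surgery clause. On either reading, a woman who has not reached menopause and has had neither operation falls within it, so the first row stands.

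The next question is whether anything else in the protocol closes the gap for a reader of the schedule.

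- Footnotes g, i, j, l, m, o and p to Table 6-1 each send the reader to a numbered section. Footnote f sends the reader nowhere and reads as complete.
- Section 6.2 has no subsection on pregnancy testing, and Table 6-2 lists no pregnancy analyte.
- Section 5.8 refers back to exclusions 10 and 11. It does not refer forward to Table 6-1.

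Nothing extends footnote f to the omitted group or points from it to Section 5.8.

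On size, the documents give no count of women who have not reached menopause. What they do give suggests a very small number: about 80 subjects of both sexes (Section 8.2), a minimum age of 55, and an expectation in Section 3.2.1.1 of a higher proportion of men than in Alzheimer's disease.

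**The case against.** The strongest reply is that this is an incomplete footnote and not a pair of orders that cannot both be obeyed. Section 5.8 is explicit about both groups. Footnote f does not say that only its group is tested, does not exempt anyone, and nothing in the protocol gives the table precedence over the text. A site that reads both will test both groups and breach neither. With entry at 55 or older, there may be no such woman in the trial at all.

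Most of this stands, and it sets the weight of the point. It does not remove the mismatch: the schedule and the text describe different groups for the same required test, and the schedule gives no sign that the text asks for more.

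A reader might also infer three stronger things that the documents do not support.

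- **That exclusion 11 itself requires the test.** It does not. It excludes on a positive result and so presupposes a test; the explicit requirement is in Section 5.8. Its contraception limb can be assessed without any test.
- **That every woman in the omitted group would be dosed untested.** That follows only if a site uses footnote f and disregards Section 5.8.
- **That a single Screening test, up to 35 days before Day 1 and with none scheduled later, contradicts the rule against exposure in pregnancy.** It does not. Section 5.8 itself asks only for a test during Screening, and Table 6-1 schedules exactly that. The same section covers the later period with contraception from before the first dose to 91 days after the last, and with discontinuation if pregnancy occurs. The 35 days is the extended Screening limit, which applies when a scan is needed; the usual limit is 21 days.

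**Conclusion.** The inconsistency is real, and minor. Footnote f names one of the two groups that Section 5.8 requires to have a negative Screening test. The missing group, women of child-bearing potential who have not reached menopause, is also within exclusion 11. The practical consequence, an untested woman being dosed, depends on a site working from the schedule alone. The number of women exposed to that risk is very small on the age criterion, but it cannot be stated from the documents and no figure is assumed here. The point is worth correcting because it concerns an eligibility and safety instruction and the correction is cheap.

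**What to change.** Reconcile Table 6-1 footnote f, Section 5.8 and exclusion criterion 11 (in Section 4.2 and in the Synopsis) so that all of them name the same group of women. Which women are to be tested is for the sponsor to settle. Once that is settled, one way to keep the passages aligned is for footnote f to refer to Section 5.8 in place of its own description. The cost is about one footnote sentence, with matching wording elsewhere if needed, and possibly a urine or serum test in very few subjects. No change to the design, sample size or analysis follows.

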6.2. Study Assessments

The subject or subject's legally authorized representative must provide written informed consent before the performance of any study-related procedures.

6.2.1. Baseline and Disease Characteristics

Details regarding DLB history, including method(s) of diagnosis will be collected during Screening, as specified in the eCRF. Subjects without documentation of prior diagnostic DLB tests (DaTscan and/or known amyloid biomarker status) are to have such tests performed during Screening (see Section 6.2.3).

6.2.2. Computed Tomography (CT) / Magnetic Resonance Imaging (MRI)

The subject must have had MRI or CT scan within 3 years of Screening, with findings negative for evidence of other neurodegenerative or other brain disease that could account for their cognitive symptoms. MRI/CT results should be available and reviewed before Screening diagnostic tests are performed. If MRI or CT has not been performed within 3 years before Screening and/or results are not available, MRI or CT scan must be performed as part of Screening to exclude other disease.

6.2.3. DaTscan (if Required)

Subjects are required to have a prior DaTscan (i.e., single-photon emission computed tomography [SPECT] with Ioflupane I 123 Injection) to be eligible for study participation.

The DaTscan is a radiopharmaceutical indicated for striatal dopamine transporter visualization using SPECT brain imaging. Ioflupane I 123 Injection is to be administered and SPECT imaging is to be performed and interpreted per the prescribing information (GE Healthcare, 2015). If a DaTscan has not been performed within the previous 2 years, it is to be performed during Screening **only after** subject has been deemed eligible based on all other inclusion/exclusion criteria (e.g., medical history, laboratory testing) and prior to randomization.

Note that if DaTscan results are negative (i.e., no evidence of reduced uptake in the basal ganglia), the subject is required to have historical PSG-verified RBD to be eligible for study participation.

6.2.4. Cognitive Function Tests

Cognitive function tests include a Neuropsychological Test Battery (NTB) as well as the Letter Fluency Test and Category Fluency Test (CFT), which are all components of the primary objective/endpoint to assess attention, executive function, and visuospatial function.

Cognitive function tests to be performed as components of the secondary objective include the CDR-SB, MMSE, NPI-10, Timed Up and Go (TUG), and International Shopping List Test (ISLT).

At Baseline and on any visits at which both NTB and other cognitive tests are conducted, the NTB should be performed prior to the other tests.

6.2.4.1. Neuropsychological Test Battery (NTB)

The NTB includes:

- Cogstate Detection test (DET)
- Cogstate Identification test (IDN)

- Cogstate One Card Learning test (OCL)
- Cogstate One Back test (ONB)
- Letter Fluency Test: The Letter Fluency Test is a measure of phonemic fluency and is a subtest of the Multilingual Aphasia Examination (Benton et al, 1994). The LFT uses the 3-letter set of F, A, and S or C, F, and L to assess phonemic fluency. Individuals are given 1 minute to name as many words as possible beginning with one of the letters. The procedure is then repeated for the remaining two letters. The administration of phonemic and semantic fluency (CFT) takes approximately 5 minutes. Admissible responses are summed and compared to a normative sample.
- Category Fluency Test (CFT): The CFT is a measure of verbal fluency and is sometimes called semantic fluency. In the standard version of the task, participants are given 1 minute to produce as many unique words as possible within a category. The subject's score is the number of unique correct words.

6.2.4.2. Clinical Dementia Rating Scale – Sum of Boxes (CDR-SB)

The Clinical Dementia Rating Scale (CDR) (Hughes, 1982) is a semi-structured interview resulting in a semi-quantitative scoring of cognitive impairment in milder and more progressed forms of dementia. It is sensitive in both AD dementia and Mild Cognitive Impairment, and is an approved regulatory endpoint recognized by the FDA. The CDR yields both a global score (CDR-GS) and Sum of Boxes score (CDR-SB). While the CDR-GS is typically utilized for staging purposes, the CDR-SB score is a more detailed quantitative general index than the CDR-GS and it provides more information than the CDR total score in cases of mild dementia (O'Bryant, et al, 2010).

The CDR interview is to be conducted with the subject and Caregiver by an experienced and certified clinician at the time points specified in Table 6-1.

6.2.4.3. Mini-Mental State Examination (MMSE)

The MMSE (Folstein et al, 1975) consists of 11 tests of orientation, memory (recent and immediate), concentration, language, and praxis. Scores range from 0 to 30, with lower scores indicating greater cognitive impairment. It is based on the performance of the subject and takes approximately 5 to 10 minutes to administer.

Standardized MMSE will be conducted by the Investigator or designee at the time points specified in Table 6-1.

6.2.4.4. International Shopping List Test (ISLT)

Word learning tests have been commonly utilized to assess episodic memory. In DLB, the recognition component is considered to be of particular utility (Wesnes et al, 2015). The ISLT is one such word learning test that has been utilized in a number of proof-of-concept clinical studies with novel therapeutics (Nathan et al, 2013; Maher-Edwards et al, 2015). Immediate and Delayed Recall, as well as Recognition, will be assessed.

6.2.4.5. 10-item Neuro-Psychiatric Inventory (NPI-10)

The NPI-10 is designed to assess psychopathology in the person with dementia and to help distinguish between the different causes of dementia. The NPI-10 examines 10 sub-domains of behavioral functioning: delusions, hallucinations, agitation/aggression, dysphoria, anxiety, euphoria, apathy,

disinhibition, irritability/lability, and aberrant motor activity. For this study, the following domains are of specific interest: depression (dysphoria), anxiety, hallucinations, and agitation/aggression. The NPI-10 is administrated to caregivers of dementia subjects. A screening question is asked about each included subdomain. If the responses to these questions indicate that the subject has problems with a particular subdomain of behavior, the caregiver is only then asked all the questions about that domain, rating the frequency of the symptoms on a 4-point scale, their severity on a 3-point scale, and the distress the symptom causes them on a 5-point scale (Cummings, 1997). The NPI-10 takes approximately 10 minutes to complete.

6.2.5. Timed Up and Go Test (TUG)

The Timed Up and Go Test is designed to assess mobility. It measures the time in seconds for a person to rise from sitting from a standard arm chair, walk 3 meters, turn, walk back to the chair, and sit down. The subject wears regular footwear and uses his/her customary walking aid. A score of >15 seconds indicates client has increased risk of falls. The test takes 1 to 2 minutes to complete.

The Timed Up and Go Test is to be administered at the time points specified in Table 6-1.

6.2.6. Columbia-Suicide Severity Rating Scale (C-SSRS)

The C-SSRS is a clinician-administered instrument that assesses suicidal ideation and behavior (Posner et al, 2011). The "Baseline" version of the instrument will be administered to subjects during Screening, and the "Since Last Visit" version will be used at subsequent time points specified in Table 6-1.

6.2.7. Electroencephalography (EEG)

Quantitative electroencephalography (qEEG) will be performed with the subject awake in accordance with the 10-20 International System of Electrode placement at the time points specified in Table 6-1 according to a standard protocol that will be provided in a separate EEG manual. Slowing of the dominant frequency band by qEEG over posterior aspects of the brain has been recognized to be prominent in DLB (Olde Dubbelink et al 2013; Peraza et al, 2018), and various patterns have been identified to differentiate DLB from AD. EEG has also been recognized to be potential biomarker for DLB in the most recent consensus report of the DLB consortium (McKeith et al, 2017).

